8.1 Training and Certification

All investigators will be certified by Intermountain Healthcare standard by CITI.

Staff at the hospital (DRMC) and participating provider's offices will be trained prior to initiation of the study. Training will be done by the study investigators and include reviewing the protocol, and the process.

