2.2 Purpose and Rationale for Study

This trial is looking at patient satisfaction and cost comparison between inpatient and outpatient preinduction cervical ripening. The method will be compared with inpatient pre-induction cervical ripening and patients admitted to the hospital in labor. Time from initiation of method, time in labor and delivery and time from onset of labor to delivery, and rate of achieving a vaginal delivery within 24 hours will be evaluated.

This protocol outlines a randomized trial of 200 women evaluating placement of Cervidil to the posterior vaginal fornix to soften the cervix in preparation for induction of labor. 100 patients will be randomized into the inpatient cervical ripening arm, and 100 to the outpatient cervical ripening arm. The study will not be powered for fetal or newborn mortality.

Increasing patient comfort, patient satisfaction, and inpatient costs will benefit future patients and healthcare for women who require/desire induction of labor.

2.3 Product being investigated:

Cervidil (outpatient cervical ripening) – Cervidil

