2.4 Risks and Benefits to Participants

2.4.1 Risks to Participants

Cervical ripening has been studied extensively using Cervidil.

Risks as described in the product insert as revised February 2016 include:

- 1) Uterine hyperstimulation with fetal distress.
- 2) Uterine hyperstimulation without fetal distress
- 3) Fetal distress without uterine hyperstimulation

Several studies have shown that there have been no cases of fetal distress occurring after 2 hours of placement of dinoprostone. (Kamerling et al., 2003), (O'Brien, Mercer, Cleary, & Sibai, 1995), (Salvador, Simpson, & Cundiff, 2009). Salvador et. al. show that hyperstimulation resolved within 15 minutes after removal of Cervidil. There were no serious complications when patients were sent home after 1 hour of monitoring. (add (Salvador et al., 2009). Most of the patients in this study would otherwise have inpatient cervical ripening with Cervidil, or a different mechanism with similar risk. Thus there would be minimal additional increased risk to the study participants. The risk of hyperstimulation is decreased because the participants and healthcare personnel would both be trained to remove the insert with any sign of hyperstimulation. The term hyperstimulation is no longer used in most clinical settings and has been supplanted with the term uterine tachsystole. (Macones, Hankins, Spong, Hauth, & Moore, 2008) Tachysystole is when there are more than five contractions in 10 minutes, averaged over 30 minutes. Hyperstimulation is used here as that was the term used in the original documents.

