3.6 Randomization Method

Women will be randomized to either an inpatient or outpatient cervical ripening procedure using a computer generated randomization scheme through REDCap.

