4.2 Study Procedures

Eligible and consenting patients will be randomized by a certified research staff member using an internet based randomization system maintained by the Women and Newborn Research department. The patient will be assigned to either the inpatient or outpatient cervical ripening group. Patients will be consented and randomized at the time the patient is being scheduled for their induction. If for any reason a research staff member is unavailable to consent the patient at the time the induction is being scheduled, a time will be set for the Cervidil placement as well as a time for the induction and consent/randomization will be scheduled prior to Cervidil placement. If they are randomized to the "inpatient group" then the following induction appointment will be cancelled.

When the participant comes in for their scheduled induction, eligibility criteria will be verified again.

4.2.1 For participants randomized to the Outpatient cervical ripening arm:

- The patient will be an outpatient in L&D ("place in observation" status in iCentra) and placed on the fetal monitor. The clinician or hospitalist will perform an ultrasound for assessment of amniotic fluid volume by deepest vertical pocket (DVP) and review the fetal heart tracing. If the fetal heart rate is reactive (Category I) and the DVP is > 2cm the procedure may proceed once ordered by the attending obstetric provider or OB hospitalist.
- 2) Nursing or research staff member completes the outpatient cervical ripening case report form (CRF).
- 3) The cervix is examined and Bishop score is documented: Requirements of exam to do cervical ripening
 - a. Cervix is dilated less than 3cm
 - b. Presenting part is vertex
 - c. The provider places the Cervidil into the posterior vaginal fornix with the string at the introitus.

- d. The provider is available for immediate phone consultation by the patient or nursing staff and is readily available to L&D.
- 4) The patient is watched with continuous fetal monitoring for 2 hours.
- 5) The patient is discharged to home if all of the following are present:
 - a. Category 1 tracing X2 hours.
 - b. No vaginal bleeding
 - c. Normal maternal vital signs.
 - d. Intact BOW
 - e. Less than 1 contraction every 10 minutes at the time of discharge.

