5.1 Data Relevant to the Primary Outcome

5.1.1 Sample Size and Power

- 1. 200 women randomized to two groups for comparison will be enrolled in the study to participate in the research group (receiving Cervidil insert). Data will be collected on the comparison group (all patients admitted cervical ripening and induction of labor) during the same time period.
- 2. With 200 patients in each group a standard two sample t test has 95% power to detect a difference of 0.36 times the standard deviation and 80% power to detect differences of 0.28 times the standard deviation. For example, if the mean time from admitting to delivery is 10 hours with a standard deviation of 2 hours (meaning that most (95%) times are in the range from 6 to 14 hours) then with this sample size we would have 95% power to detect a reduction of 43.2 minutes in the treatment group and a 80% power to detect a difference of 33.6 minutes. These numbers will differ if the true standard deviation is different from 2 hours.

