7.1.1 Participating Clinical Centers

Dixie Regional Medical Center, labor and delivery unit, and Utah Valley Hospital, labor and delivery unit will conduct this study.

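### Two hospitals run the trial, but pre-study staff training is committed at only one, and hospital and parity appear in neither the allocation scheme nor the primary analysis

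*Combined protocol and SAP*

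**What the plan says.** **Sites.** Section 7.1.1: "Dixie Regional Medical Center, labor and delivery unit, and Utah Valley Hospital, labor and delivery unit will conduct this study".

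**Training.** Section 8.1: "Staff at the hospital (DRMC) and participating provider's offices will be trained prior to initiation of the study". It continues: "Training will be done by the study investigators and include reviewing the protocol, and the process". The abbreviation DRMC is not expanded, but of the two hospitals in 7.1.1 only Dixie Regional Medical Center fits it. No training commitment names Utah Valley Hospital. Section 2.4.1 argues that the risk of hyperstimulation is lowered because "the participants and healthcare personnel would both be trained to remove the insert with any sign of hyperstimulation"; it gives no site, timing or content for that training.

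**Allocation.** Section 3.6: "Women will be randomized to either an inpatient or outpatient cervical ripening procedure using a computer generated randomization scheme through REDCap". Section 4.2 adds that women are "randomized by a certified research staff member using an internet based randomization system maintained by the Women and Newborn Research department". Neither section mentions strata, blocks or a site factor.

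**Analysis and data.** Section 5.3 makes the two-sample t-test primary for numeric outcomes, on the log scale if skewed, with a permutation test as fallback. Covariate adjustment is exploratory and hospital is not named. Section 6.3 lists gravidity and parity (G/TPAL) among the data elements, but not the enrolling hospital.

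**The concern.** There are two separate issues, and the first is the stronger.

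**Training.** Sections 4.2.1 and 3.7.4 give unit staff much of the work that makes home ripening safe and measurable: completing the case report form, two hours of monitoring, the discharge check, and insert removal with Bishop scoring on return. Section 4.3 relies on the nurse for event reports. Section 3.7.1 acknowledges that outpatient use is outside the package insert. If 8.1 were followed to the letter, one of the two units could start without the training that 2.4.1 counts on. The monitored events in 7.2.2 do not include staff training, so the monitoring described would not be expected to reveal the gap.

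**Site and parity.** Both are known when a woman is randomised at scheduling. The primary outcomes in 4.4.1 (time from admission to complete dilation, and costs charged) could plausibly vary with either. If neither the allocation nor the primary test accounts for them, a chance excess of one hospital or parity group in one arm goes straight into the estimate.

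**Working it through.** **1. Training: the sections side by side.** Units conducting the trial: two (7.1.1). Units whose staff are committed to training before the study: one, plus provider offices (8.1). Personnel whose training is counted as a risk control: all, with no site limit (2.4.1). The three statements agree only if 8.1 is extended to the second unit. No arithmetic applies.

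**2. The plan's own power figure.** Section 5.1.1 says: "With 200 patients in each group a standard two sample t test has 95% power to detect a difference of 0.36 times" (multiples of the SD), and gives 0.28 SD for its 80% figure. Normal approximation, two-sided 5%: power = Φ(d·√(n/2) − 1.96).
- n = 200, d = 0.36: Φ(3.60 − 1.96) = 94.95%
- n = 200, d = 0.28: Φ(2.80 − 1.96) = 79.96%
- With the example SD of 2 h: 0.36 × 120 = 43.2 min and 0.28 × 120 = 33.6 min

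All reproduce. However, section 2.2 says "100 patients will be randomized into the inpatient cervical ripening arm, and 100 to the outpatient cervical ripening arm", so I use 100 per arm below. There d = 0.36 gives Φ(2.546 − 1.96) = 72.1%. The 100-versus-200 discrepancy is a separate matter.

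**3. Chance imbalance in site share.** The site split s is not given, so it is assumed. With no stratification and 100 per arm out of N = 200, the number of women from one hospital in an arm is hypergeometric, and

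SD of the between-arm difference = √[s(1−s)(1/100 + 1/100) × 200/199].

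| Assumed split | SD (points) | P(gap ≥ 10 points) | P(gap ≥ 14 points) |
|---|---|---|---|
| 50:50 | 7.09 | 20.3% | 6.6% |
| 70:30 | 6.50 | 16.5% | 4.4% |

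Without the small 200/199 factor, the 95% range is ±1.96 × 7.07 = ±13.9 points at 50:50 and ±11.1 at 80:20. At 200 per arm and 50:50 it is ±9.8. A parity split of the same proportions would give the same figures; the documents give no parity split.

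**4. What that does to the time outcome.** The between-hospital difference g in mean time is also not given, so it is assumed. Shift in the arm difference (95% range) = 1.96 × SD × g.

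| Assumed g | 50:50 | 80:20 |
|---|---|---|
| 0.5 h | ±4.2 min | ±3.3 min |
| 1 h | ±8.3 min | ±6.7 min |
| 2 h | ±16.6 min | ±13.3 min |

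For scale, the standard error of the arm difference at 100 per arm and SD 2 h is 120 × √(2/100) = 17.0 min, and the plan's larger design difference is 43.2 min.

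**5. Power cost of leaving site out.** Take 2 h as the within-hospital SD (an assumption). The unadjusted SD is √[4 + s(1−s)g²]. For 43.2 min (0.72 h), 100 per arm and a 50:50 split:
- site in the model: SD 2.00, power 72.1%
- g = 1 h, site ignored: SD √4.25 = 2.062, power 69.5% (a loss of 2.6 points)
- g = 2 h, site ignored: SD √5 = 2.236, power 62.4% (a loss of 9.7 points)

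The 2 h SD is the plan's example for admission to delivery, whereas the primary outcome runs to complete dilation, so these figures show scale only.

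**The case against.** **On training.** A reader might infer that Utah Valley staff will be untrained. The documents do not say that. Section 8.1 omits a site; it does not exempt one. Section 2.4.1 speaks of healthcare personnel without limit, the placement, discharge and return criteria are written in 4.2 for every site, and allocation is made by certified research staff. Sections 7.2 and 7.2.2 add reviews after the first five participants and then quarterly. All of this stands, and it makes the problem an unsecured commitment rather than a demonstrated failure. It does not close the gap: 8.1 is the section that states who is trained and when, and the early reviews are not per site.

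**On stratification.** A reader might infer that allocation is unstratified. That would be read from silence: 3.6 and 4.2 do not rule out strata, and section 1.3 refers to a manual of operations that is not among the documents. The supportable statement is that no stratification is specified.

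**On bias.** A reader might also infer that the result would be biased by site. Under randomisation the imbalance is chance. It does not shift the comparison on average or raise the type I error rate, and the unadjusted standard error already contains the between-site variation. Nor do the documents show that the hospitals differ: both arms follow one health system's induction guidelines and charges come from one billing service. Simple randomisation of 200 women at two sites is defensible. This limits the second half to a matter of precision and credibility.

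**On the remedy.** Stratifying the list while keeping the plain t-test would give an overstated standard error and forfeit most of the precision gained. That is correct, so the analysis must change as well.

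**Conclusion.** The point holds in two parts of unequal weight.

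The mismatch between 7.1.1 and 8.1 is on the face of the text and should be reconciled, because 2.4.1 relies on the training. The conclusion is that training at the second hospital is not secured, not that it will be missing. It rests on reading DRMC as Dixie Regional Medical Center.

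The allocation and analysis part is a worthwhile, low-cost improvement of modest size. At 100 per arm with an even site split, site shares would differ by an SD of about 7 points. A 1 h hospital difference would then move the arm difference by up to about 8 min against a standard error of 17 min, and cost about 2.6 points of power. It becomes material only with a large hospital or parity difference, such as 2 h (about 17 min and 9.7 points). The split and the difference are both assumptions. The figures also assume that the manual of operations does not already provide for strata.

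**What to change.** - **Section 8.1:** reconcile with 7.1.1 by naming both units, and require each site's training to be complete before its first randomisation.
- **Section 3.6:** state that the REDCap list is stratified by hospital and parity (nulliparous/parous, four strata), with randomly varying block sizes concealed from the sites. Make 4.2 agree.
- **Section 6.3:** add enrolling hospital to the data elements.
- **Section 5.3:** for the numeric outcomes, make the primary analysis a linear model (on the log scale where the plan already allows it) with terms for arm, hospital and parity. If the permutation fallback is used, permute within the four strata.

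**Cost.** The same training is delivered at the second hospital, a new allocation table is built, one field is added, and there is a little more analysis work. The sample size does not change. Blocking makes allocation slightly more predictable in a trial where setting cannot be masked; concealed, varying block sizes limit this.

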8.2 Recruitment and Data Collection Period

The study sign-up period is anticipated to be up to 3 years and the participants will be followed from sign up until 3 months after delivery.

